Study Rationale	
Impaired balance in activation between left and right prefrontal cortex has been described in patients with PMDD, consistent with its view as a network disorder. In particular, similar to major depressive disorder, the balance between alpha oscillation power in the left and the right hemisphere is shifted towards the left in patients with PMDD, more so during the luteal phase. We hypothesize that normalization of alpha oscillations in women with PMDD may be accomplished with brain stimulation by application of weak electric currents through transcranial alternating current stimulation (tACS), thereby altering the temporal activity structure of electric signaling in the brain. In this study, we will obtain electroencephalograms (EEGs) to assess whether a single session of tACS will enhance bilateral alpha synchronization (8-12 Hz) (by reducing left prefrontal alpha power) and whether this varies by menstrual cycle phase. An exploratory objective will be to examine the severity of the PMDD symptoms collected daily during the stimulation cycle compared with the baseline cycle.

Study Objective(s)	
Primary
 
 To determine whether a single session of tACS will reduce left prefrontal alpha power and thereby restore alpha symmetry 
Secondary
 
 To determine whether the impact of tACS on alpha power and distribution differs across menstrual cycle phases
Test Article(s) (If Applicable)	
XCSITE 100 Stimulator
 
The device consists of the following main components/subsystems: 1. Tablet with user interface application (App) 2. Microprocessor 3. Function generator chip 4. Voltage controlled current source 5. Safety circuitry
 
First, the stimulation parameters are specified by the user through the app. The parameters are: 1. tDCS/tACS 2. Number of channels 3. Amplitude 4. Test duration 5. Frequency (for tACS) 6. Password. Next, the parameters are sent via Bluetooth to the microprocessor. The microprocessor interprets these parameters, and programs the function generator chip accordingly through a SPI. The function generator then creates the programmed waveform, which is ultimately a voltage signal. The voltage signal is applied to a voltage controlled current source, which generates the specified amount of current through an arbitrary load resistance.

Study Design	Repeated measure, open-label trial

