Study Phases Screening Study Treatment	
(1) Screening: Subjects with a diagnosis of PMDD confirmed by participation in a PMDD diagnostic study will be screened for eligibility in the tACS Study and review the informed consent forms. (2) Intervention: After consent is obtained, subjects will be asked to notify study personnel when they begin menstruating. If the subject is randomized to receive tACS in the follicular phase first, they will schedule a tACS session within 9 days of the onset of menses. If they are randomized to receive tACS in the luteal phase first, the subjects will then perform a home urine ovulation test every morning until they receive a positive result, at which point they will schedule their tACS session 9-13 days after the positive test result. Each stimulation session will last 40 minutes, plus the time it takes to place electrodes. EEG will be recorded before and after stimulation. At the end of the first session, subjects will be instructed to complete daily symptom rating scales for one completed menstrual cycle, or about 28-32 days. The second tACS session will be identical to the first, except it will occur in the opposite menstrual cycle phase as the first session.

Efficacy Evaluations	Primary efficacy measurement will be changes in left prefrontal alpha power or distribution (asymmetry) following tACS
Pharmacokinetic Evaluations	Not Applicable
Safety Evaluations	Primary measurements that will be used to assess safety:

-
- Subject semi-structured interview
 - Physical symptom items on the Daily Record of Severity of Problems (DRSP)
-

Statistical And Analytic Plan

We will use a t-test of pre-post changes to examine effects of tACS on left prefrontal alpha oscillations (primary outcome) and differences in effects as function of menstrual cycle phase (secondary outcome). There will be two levels of each of the two repeated within-subjects measures (pre vs post stimulation and follicular vs luteal phase). Order of administration will be assessed by considering order as a between- subjects variable.

DATA AND SAFETY MONITORING PLAN

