Protocol History: This protocol was originally designed to test the therapeutic efficacy of tACS in PMDD in a double blind, randomized, sham controlled, cross-over study of 5 tACS sessions. We were unable to recruit subjects, largely consequent to the many daily treatment sessions required. We subsequently changed the primary focus of the study to that of determining whether a single session of tACS engaged left prefrontal cortical alpha oscillations and, by reducing them, reduced alpha asymmetry. We further asked whether this effect was menstrual cycle phase-dependent. If target engagement was demonstrated, we then intended to perform a follow-up study to assess clinical efficacy, particularly but not exclusively if there were any evidence for reduction of mood symptoms on the exploratory analysis.

Name and Description of Investigational Product or Intervention

XCSITE100 Stimulator

We will be using the XCSITE100 stimulator designed in the [name] Lab for investigational purposes. The device is not implanted and has not been designed for or being used to support or sustain human life. This device does not have a potential for serious risk to the health, safety, or welfare of the participant. There has never been an instance of serious side-effect reported due to the use of transcranial brain stimulation. Previous studies in the [name] lab that used comparable devices (i.e., the commercial, CE-certified NeuroConn Plus stimulator) have always been classified as “non-significant risk” by the full UNC IRB. The NeuroConn Plus stimulator and the XCSITE100 stimulator are electrically equivalent and provide the same stimulation.

The XCSITE100 is the first non-invasive brain stimulator designed for research purposes to provide an active sham for tACS and record the stimulation output for later validation. This stimulator may apply either tDCS or tACS for up to 40 minutes (2400 seconds) with appropriate current ramp-up at the beginning of stimulation and ramp-down at the end of stimulation. Both tDCS and tACS may be applied for currents between 100 μ A and 2 mA (peak-to-peak for tACS).

The stimulator has two main components:

1. Android tablet with user interface application (i.e., App)
2. Stimulator with:
 - a. Microprocessor

- b. Function generator chip
- c. Voltage controlled current source
- d. Safety circuitry

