2 STUDY OBJECTIVES

The purpose of this study is to determine in women with PMDD whether a single session of tACS will alter left prefrontal alpha oscillatory power (enhance bifrontal symmetry, which is described as abnormal in PMDD). The secondary objective will be to determine if this ‘target engagement’ will differ by menstrual cycle phase. Our exploratory objective will be to examine whether changes in cortical dynamics will be associated with symptom reduction relative to baseline, pre-stimulation levels (obtained in the diagnostic feeder protocol IRB# 05-3000).

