3 INVESTIGATIONAL PLAN

3.1 Study Design

Repeated measure, open-label study design.

Overview of study phases:

- **Screening/Baseline:** subjects will be followed for three months in a related protocol to document that subjects meet criteria for PMDD, showing affective symptoms of requisite severity as present during the luteal phase and relatively absent during the follicular phase.
- **Intervention/Treatment:** a single 40-minute session of tACS, administered once each in the follicular and luteal phases of the menstrual cycle

- **Follow up:** subjects will be followed with daily ratings until completion of the menstrual cycle following the second tACS. Any subject endorsing suicidal ideation, severe deterioration of mood, or distressing somatic symptoms on daily rating forms will be referred to [name] for acute evaluation and determination of appropriate subsequent clinical response.
- **Unscheduled Visits:** not applicable

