3.4 Study Population

-Inclusion and Exclusion Criteria

Subjects will be women with PMDD. All subjects will have had their diagnoses confirmed by participation in our diagnostic study. The diagnosis requires demonstration of at least a 30% increase in symptom ratings in the seven days preceding menses compared with the seven days following the cessation of menses in two of three menstrual cycles.

In addition to PMDD diagnosis, all women enrolled must also meet the following criteria:

Inclusion Criteria:

- Age 18-52
- Have participated in our PMDD diagnostic study
- Regularly menstruating without hormonal contraceptives (e.g., birth control pills, injections, implants, progestin IUDs)
- Medication free or regularly taking medication that has no effect on the nervous system
- Not currently pregnant or planning to become pregnant
- With sufficient resource to prevent pregnancy

Exclusion Criteria:

- Brain surgery or brain implants (e.g., cochlear implants or aneurysm clips)
- Neurologic disease (e.g., epilepsy or a brain tumor)
- Traumatic brain injury
- Pregnant or nursing
- Any unstable medical illness (e.g., congestive heart failure or end-stage kidney disease)
- History of severe or recurrent substance use disorder, or any substance abuse within 2 years of study enrollment
- History of suicidal behavior within 5 years of study enrollment
- UNC Psychiatry faculty, employee, or trainee
-

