6 STATISTICAL CONSIDERATION

This is repeated, single intervention (tACS) administered during the follicular and luteal phase. Change in left prefrontal alpha power on EEG is the primary outcomes. Effect of menstrual cycle phase is the secondary outcome. We plan to analyze our data using a repeated measure analysis of variance (ANOVA-R), with two within subject variables, each with two levels: time (pre vs post tACS), and menstrual cycle phase (follicular vs luteal). We will assess any effects of order of administration (follicular first vs luteal first) by including order as a between-subjects variable.

Clinical symptoms will be quantified as the mean of daily nighttime ratings (individual symptoms rated from 1 to 6) collected in the follicular (days 4 – 9) and luteal phases (the 6 days preceding menses) as recorded in the DRSP.

Decrease in left prefrontal power (reflection of reduction in alpha asymmetry) will be calculated by comparing results from the following time points: 1) immediately before the stimulation and 2) immediately following the stimulation in each of the follicular and luteal phases.

The main intent of this study is to conduct a pilot study, the results of which could be used in a larger trial that is appropriately powered for efficacy. Nonetheless, we intend to determine whether tACS influences alpha coherence on EEG. Due to the novelty of the application and the treatment strategy, we do not have all the required parameters to estimate the power for the repeated measure design on alpha coherence on EEG. However, the primary purpose is to demonstrate tACS associated changes in alpha coherence and whether that differs by cycle phase. The aim to demonstrate ‘target engagement’ does not necessarily lend itself to traditional power calculations and we will rely on [name] extensive experience with analyzing these data. In his experience, he is confident that if, in fact, if there are menstrual cycle differences in alpha coherence, 20 participants will be sufficient to demonstrate that effect.

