6.3 Statistical Methods

Baseline Data: alpha oscillations in left frontal cortex before stimulation; severity of luteal phase symptoms in screening DRSP.

Efficacy Analysis: This is repeated, single intervention (tACS) administered during the follicular and luteal phase. Change in left prefrontal alpha power on EEG is the primary outcome. Effect of menstrual cycle phase is the secondary outcome. We will use a t-test of pre-post changes to examine effects of tACS on left prefrontal alpha oscillations (primary outcome) and differences in effects as function of menstrual cycle phase (secondary outcome). There will be two levels of each of the two repeated within-subjects measures (pre vs post stimulation and follicular vs luteal phase). Order of administration will be assessed by considering order as a between- subjects variable.

Exploratory analysis: Assessment of possible changes in mood will be assessed with linear mixed model regression analysis comparing mean luteal phase core affective symptoms (depression, irritability) after stimulation with means during baseline.

Pharmacokinetic Analysis (if applicable): not applicable

Safety Analysis - The PI will review any adverse effects and will quarterly review aggregated data, which will be recorded descriptively. Safety/ Tolerability will be assessed in two ways: 1) with somatic symptoms contained within the DRSP, completed daily, and with symptoms reviewed daily by the research coordinator. Any symptoms of moderate or greater severity appearing proximate to the tACS session will be reported to the PI. 2) with a semi-structured interview at the end of each tACS session, inquiring about possible side effects during the procedure (e.g., tingling, flickering lights, itching, burning sensation, headache, neck pain, scalp pain). Side effects of moderate or greater severity will be reported to the PI, who will also review aggregate data at the end of the experiment.

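### The exploratory mood comparison uses as its baseline the ratings that selected the women, with no control, so some fall is expected without any effect; the Section 2 association has no analysis

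*Combined protocol and SAP*

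**What the plan says.** **Analysis.** The only mood analysis, in Section 6.3, is a linear mixed model "comparing mean luteal phase core affective symptoms (depression, irritability) after stimulation with means during baseline". It contains no EEG variable. Section 6 defines the symptom score as a mean of nightly DRSP ratings over set windows, the premenstrual one being given as "luteal phases (the 6 days preceding menses".

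**Objective.** Section 2 says the aim is to "examine whether changes in cortical dynamics will be associated with symptom reduction relative to baseline, pre-stimulation levels". The synopsis (Study Rationale) says it is to "examine the severity of the PMDD symptoms collected daily during the stimulation cycle compared with the baseline cycle", and Section 1 gives a similar before-after version.

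**Baseline and selection.** Sections 1, 2 and 6.3 take baseline symptoms from the diagnostic (screening) study. Entry rests on ratings from that study. Section 3.4 requires two qualifying cycles out of three, each with "at least a 30% increase in symptom ratings in the seven days preceding menses compared with the seven days following the cessation of menses". Section 4.1 adds a score of at least 4 on the 1-6 scale, on two luteal days, for a core emotional symptom. Section 11 repeats the 30% rule.

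**Design and timing.** Section 3.1 describes an open-label, repeated-measures study in which every woman is stimulated in both phases. The luteal session falls 9-13 days after a positive ovulation test (Section 4.1), and ratings begin after the first session (Sections 4.1 and 4.2). On how long they run, the synopsis says "complete daily symptom rating scales for one completed menstrual cycle, or about 28-32 days" and Section 3.1 says "subjects will be followed with daily ratings until completion of the menstrual cycle following the second tACS". Section 4 has them daily throughout the study.

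**Use.** Section 1 (Protocol History) intends a follow-up efficacy study if target engagement is shown, "particularly but not exclusively if there were any evidence for reduction of mood symptoms on the exploratory analysis".

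**The concern.** Women enter because their recorded luteal symptoms were high. Part of any high reading is cycle-specific, so the next cycle tends to be lower whether or not they are stimulated. With no sham or untreated cycle, the comparison cannot separate that fall from a treatment effect. The plan does not say which screening cycles form the baseline, and that choice strongly affects the size of the artefact.

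Two further gaps affect the same analysis. The association named in Section 2 would bear more directly on mechanism than a mean change does, but nothing in Section 6.3 estimates it. And the post-stimulation period is not tied to a session, so it can mean different exposure for women randomised to different orders.

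At stake is how a mood reduction is read when the follow-up efficacy study is considered.

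**Working it through.** **1. Plan figures.** The plan gives no alpha, SD, effect size or power for mood, so there is nothing to reproduce. Its only relevant number is the sample size: 20 completers from 22 enrolled (20 × 1.10 = 22; 20 / 0.90 = 22.2). The checks below use n = 20.

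**2. Simple model of regression to the mean.** Assumptions: four exchangeable normal cycles with correlation r (three screening, one later); no treatment effect; entry when at least two of three screening cycles exceed the screened mean, or 0.5 SD above it. When baseline is the mean of all three cycles,

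expected fall = (1 − r)/(1 + 2r) × (selected baseline mean − screened mean).

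The multiplier is 0.5/2.0 = 0.25 at r = 0.5 and 0.3/2.4 = 0.125 at r = 0.7. At r = 0.5 with the lower threshold, the selected women's three-cycle mean lies about 0.62 SD above the screened mean, so the fall is 0.25 × 0.62 ≈ 0.155 SD. Simulated falls are below. False improvement means a two-sided 5% paired test at n = 20 that is significant for a reduction (nominal 2.5%).

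| r | Threshold (SD) | Qualifying cycles only: fall (SD), false improvement | All three cycles: fall (SD), false improvement |
|---|---|---|---|
| 0.5 | 0 | 0.355, 45% | 0.155, 12% |
| 0.5 | 0.5 | 0.479, 70% | 0.233, 23% |
| 0.7 | 0 | 0.207, 27% | 0.087, 8% |
| 0.7 | 0.5 | 0.282, 47% | 0.133, 15% |

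A rerun agreed to within about 1.5 percentage points.

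**3. Model closer to the entry rule.** A cycle qualifies with at least two of seven luteal days at 4 or more and a luteal mean at least 1.3 times the follicular mean; two of three cycles must qualify. Assumptions: luteal cycle mean before selection 2.5 to 4.0, variance 0.8, intraclass correlation 0.3 to 0.7, daily SD 1.0, follicular mean 1.6, later cycle scored over six days. A paired test stands in for a random-intercept model with one baseline and one later mean.

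| Luteal mean before selection | Qualifying cycles only: fall (points), false improvement | All three cycles: fall (points), false improvement |
|---|---|---|
| 2.5 | 0.32-0.59, 47-80% | 0.15-0.30, 14-31% |
| 3.0 | 0.23-0.43, 28-51% | 0.10-0.19, 8-14% |
| 3.5 | 0.15-0.28, 14-25% | 0.05-0.10, 5-6% |
| 4.0 | 0.09-0.15, 8-10% | 0.03, 3-4% |

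The fall is largest when symptoms sit near the entry threshold. It nearly vanishes when they sit well above it and all three cycles are used.

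**4. Premenstrual window against the luteal session.** Let menses start L days after the positive test (assumed 12 to 16). The six-day window is days L − 6 to L − 1. At L = 14 it is days 8-13, so a session on day 9, 10, 11, 12 or 13 leaves 1, 2, 3, 4 or 5 of the six days before stimulation. For L = 12, 13, 14, 15 and 16, the window contains days on both sides of the session for 3, 4, 5, 4 and 3 of the five permitted session days: 19 of 25 combinations. In follicular-first women the whole window follows session 1 but usually straddles session 2. In luteal-first women the days before session 1 are not rated in the trial.

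**5. Length of rating.** Take a luteal-first woman with a 28-day cycle and a positive test on day 14, so her session is on day 23-27. Counting from the session day, 28 days of rating end on day 22-26 of the next cycle and capture 0 to 4 of its last six days (days 23-28). Thirty-two days end on day 26-30 and capture 4 to 6.

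**6. Objectives side by side.** The synopsis and Section 1 versions ask for a before-after comparison, which Section 6.3 supplies. The Section 2 version needs EEG change as a predictor of symptom change, which Section 6.3 does not supply.

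**The case against.** The strongest reply is that this is an exploratory analysis in a declared pilot, that it leaves the EEG endpoints untouched, and that Section 6.3 does deliver the exploratory objective given in the synopsis and Section 1. All of that stands, and it limits the weight of the point. It does not answer the selection problem or supply the Section 2 analysis.

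Several stronger readings are tempting, and the documents do not support them:

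- *The mood analysis misses its objective altogether.* It misses the Section 2 version only. The defect is two versions of one objective, with one of them analysed.
- *The straddled window causes the regression to the mean.* It does not; selection without a control does. The straddle is a separate ambiguity about exposure.
- *Baseline is scored over seven days and the trial over six.* Seven days is the eligibility window. Section 6 does not confine the six-day window to trial cycles, and no section sets a seven-day baseline for analysis.
- *Luteal-first women will lose most of their next premenstrual ratings.* The count of 0 to 4 days is the 28-day end of the synopsis range. At 32 days it is 4 to 6, and Sections 3.1 and 4 may cover more. This is an inconsistency, not established data loss.
- *A false mood signal would trigger the follow-up study.* Section 1 makes target engagement the first condition; mood adds support.
- *The percentages describe this trial.* They rest on assumed correlations, severity and selection. The plan does not say that baseline means the qualifying cycles only, and it sets no significance rule for mood.

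**Conclusion.** The concern holds in this form. Some fall in luteal symptoms is expected with no effect, because the baseline ratings also selected the women and nothing controls for that. The direction is secure; the size is not. Across the two models, false improvement at n = 20 runs from 8% to 80% with qualifying cycles as baseline and from 3% to 31% with all three, against a nominal 2.5%. These ranges depend on the assumed cycle-to-cycle correlation and on how far typical severity lies above the entry threshold, neither of which the plan gives.

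Two lesser points need no assumption about those quantities: the Section 2 association has no analysis, and the post-stimulation period is not defined by session while the sections disagree on rating duration. The usual straddling of the luteal session does assume 12 to 16 days from positive test to menses. The matter is worth correcting because of the weight Section 1 gives to a mood reduction.

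**What to change.** 1. Add an analysis for the Section 2 objective: regress each woman's DRSP change on her change in left prefrontal log alpha power, with order as a covariate, naming in advance which session's EEG change is used. Regression to the mean then falls mainly in the intercept, provided EEG change is unrelated to how extreme the baseline was. Report an estimate with a confidence interval. With 20 women, 80% power for a simple correlation needs about tanh[(1.96 + 0.84)/√17] = 0.59, so a test alone would say little.
2. Compute baseline from all screening cycles, not only the qualifying ones, and apply the six-day window of Section 6 in both periods.
3. State that the uncontrolled mean change is descriptive and will not by itself count as evidence of symptom benefit for the follow-up decision. Step 2 reduces the bias but does not remove it.
4. Define the post-stimulation window by session and order, and reconcile the synopsis with Sections 3.1, 4, 4.1 and 4.2 on when ratings start and stop. A window after both sessions would take follicular-first women out of the stimulation cycle named in the synopsis and beyond the roughly one-month participation in the synopsis and Section 3.3. If that window is chosen, those passages must change too.

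The cost is SAP wording, minor reprocessing of daily ratings already collected, and a weaker mood claim. A later window, if chosen, would lengthen rating for some women.

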Previous studies employing tACS, a non-invasive, non-pharmacologic procedure, have shown tACS to be safe and devoid of serious adverse effects. However, tACS does have some mild side effects, such as transient mild tingling, burning, or itching under the electrode sites. In our experience to date, subjects have reported either absent or mild side effects, and there was no difference between the groups with the exception of “flickering lights” (or phosphenes, $p = 0.014$) (Alexander et al., in preparation). Nonetheless, we will employ the following safety measures: subjects will be told that they can stop the stimulation at any time during the procedure and research personnel present during these sessions will also check in with the subject periodically during the stimulation to see whether they are comfortable.. Each subject will receive a semi-structured interview at the conclusion of the stimulation, and any side effects of greater than mild severity will be reported to the study PI. Possible side effects will be more formally evaluated with the daily rating forms, which will ask the subject to rate physical symptoms such as fatigue, headache, pain as well as any symptoms (which the subject can provide in text in the DRSP). The study coordinator will review the subjects’ daily rating forms daily. The PI will review adverse events and side effects in an aggregate format across all subjects enrolled on a quarterly basis. Substantial clinical worsening (compared with the baseline cycles) may result in a subject’s discontinuation from the study, at the discretion of the PI. Development of suicidal ideation more than just passive ideation (i.e., sometimes I feel like life is not worth living – not uncommon in women with PMDD in their symptomatic phase) for any reason or any unanticipated serious side effect will result in the subject’s discontinuation. Failure of the subject to experience symptom attenuation following the cessation of menses will result in the subject’s evaluation, discontinuation from the study, and recommendation of therapeutic intervention if required. The PI is responsible for the assessment and, where appropriate, the reporting of any adverse effects, and the PI can be reached 24/7. Finally, there is a theoretical likelihood that stimulation of neuronal circuits can lead to seizure. However, no studies have reported seizure as a side effect in recent trials of transcranial stimulation for depression or schizophrenia. To further minimize this very small, theoretical likelihood of a seizure, we screen and exclude patients with personal and family history of neurological conditions from the study.

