When comparing input of energy into the subject, both the amount of current and the area over which this current is dispersed are critically important. The value of interest is called the current density, which is the amount of current divided by the area. Our stimulation area is 25 cm². Therefore, we will use this device at 2mA, resulting in a current density of 0.08mA/cm². Our use of this transcranial current stimulation device poses 'minimal risk' to subjects because of the low current density being applied. Our application of current will result in an equivalent current density as performed in prior studies, in which subjects experienced no serious side-effects or harm. Prior studies using other brain stimulators have used a range of current densities: (Iyer, Mattu et al. 2005) used a maximum current density 0.08mA/cm², conducted at NINDS with DC stimulators, and (Groppa, Bergmann et al. 2010) used a maximum current density of 0.125mA/cm² with no reported side effects

With use of this technology, some subjects report transient tingling underneath the electrode on the scalp, itching, headache, burning sensation, and discomfort. However, a recent meta-review has

failed to find any significant difference in occurrence rates between transcranial current stimulation and sham control itching (39.3% vs. 32.9%, $p>0.05$), tingling (22.2% vs. 18.3%, $p>0.05$), headache (14.8% vs. 16.2%, $p>0.05$), burning sensation (8.7% vs. 10%, $p>0.05$) and discomfort (10.4% vs. 13.4%, $p>0.05$). (Brunoni, Amadera et al. 2011). In our experience, increased sleepiness and flickering lights were more common than sham stimulation. During stimulation, the research assistant will ask the subject about her comfort level. If the subject reports any pain, stimulation will immediately be stopped.

EEG: EEG is a commonly used measure and is not associated with adverse events. Individuals may find the electrode gel annoying, as hair will require shampooing after the conclusion of the EEG.

Embarrassment: Self-report assessments contain questions regarding sensitive personal information. This risk is necessary to assess mood symptoms and psychopathology. Subjects will be assured upon intake that only study personnel will see associated DRSP responses.

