Moderate AE: would be associated with temporary (minutes to a few days) disruption in activities of daily living, such as temporary loss of consciousness with venipuncture; worsening of migraines or headache that require bed rest; an increase in depressive symptoms; dizziness that precludes ambulation; or something of equal significance.

Severe AE: would include any event that acutely threatens the patient's health, is life-threatening, or potentially permanently disabling, or an event of equal significance.

II. Monitoring and reporting of adverse events (AEs)

The study coordinator and tACS technician will monitor side effects during and following tACS administration. Side effects consistent with moderate or severe AEs will be immediately reported to [name], who will be responsible for determining the next course of action, which might include discontinuation of the subject from the study. [name] will review aggregate reports of side effects/AEs quarterly. As the contact PI, [name] will be the one responsible to report all AEs reported as moderate or severe to the IRB and CTSC within one week.

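### No structured side-effect check before stimulation, and a safety summary that does not separate the two cycle phases or use the DRSP somatic baseline that already exists

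*Combined protocol and SAP*

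**What the plan says.** The synopsis (Safety Evaluations) names two safety measurements: a semi-structured interview and "Physical symptom items on the Daily Record of Severity of Problems (DRSP)".

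- **Interview.** The Data and Safety Monitoring Plan in the synopsis states: "Each subject will receive a semi-structured interview at the conclusion of the stimulation". Section 6.3 (Safety Analysis) places it in the same position, "with a semi-structured interview at the end of each tACS session, inquiring about possible side effects during the procedure", and gives seven example symptoms, headache and neck pain among them.
- **Monitoring by staff.** Section 9, part II: "The study coordinator and tACS technician will monitor side effects during and following tACS administration". Section 1.1 adds an informal check: "During stimulation, the research assistant will ask the subject about her comfort level".
- **DRSP.** Sections 4.1 and 4.2 and the synopsis have participants begin their daily ratings after the first session. Sections 4 and 5 say more loosely that ratings run daily through the study. The somatic rule in section 6.3 is: "Any symptoms of moderate or greater severity appearing proximate to the tACS session will be reported to the PI".
- **Summary.** Section 6.3: "The PI will review any adverse effects and will quarterly review aggregated data, which will be recorded descriptively". No breakdown by cycle phase is mentioned.

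**The concern.** There is no sham arm and no blinding, so the main reference for deciding whether a symptom is new is the woman's own state just before the current is switched on. The plan records that state for the EEG, which is taken before and after stimulation in both phases. It does not do so for side effects.

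The symptoms at risk are those a woman can bring with her. Among the section 6.3 examples these are mainly headache and neck pain. One of the two sessions is deliberately placed in the premenstrual phase, when somatic complaints are part of the condition under study. A summary that pools both sessions cannot show whether reports gather in one phase.

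What is at stake is how well the tolerability description can be read. Sections 6 and 6.4 call this a pilot whose results could feed a larger trial. Status on arrival cannot be recovered later if it was not asked.

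**Working it through.** The safety analysis states no figure of its own, so there is none to reproduce. The check is mainly a reading of what is recorded when, followed by one illustration of scale.

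**1. What is recorded around each stimulation**

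| Time | Side-effect information described | Where |
|---|---|---|
| Before session 1 | None in this study; the pre-stimulation measurement is EEG. DRSP ratings from the diagnostic study exist | 3.1, 4.1, 4.2, 5 |
| Before session 2 | Daily DRSP ratings since session 1; no interview | 4.1, 4.2 |
| During each session | Staff monitoring and comfort questions | 1.1, 9 |
| End of each session | Semi-structured interview | synopsis, 6.3 |
| After each session | Staff monitoring; daily DRSP | 4.2, 9 |

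The interview items therefore have no structured pre-stimulation value at either session. The DRSP physical items have an in-study value before session 2 but not before session 1.

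**2. What baseline material exists, and where it is used**

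- Section 3.1: three months of follow-up in the diagnostic study.
- Section 5: the DRSP used there includes a physical symptom domain.
- Section 6: follicular (days 4–9) and luteal (last 6 days before menses) windows for summarising DRSP symptoms.
- Section 6.3, Baseline Data: luteal symptom severity from the screening DRSP.
- Uses of earlier cycles: a discretionary decision to discontinue a woman who deteriorates (synopsis and section 9), and the exploratory comparison of depression and irritability (section 6.3).

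None of these is tied to the somatic safety summary. The data are available; the link is not written.

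**3. Scale of background reports**

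Inputs: 20 women (section 3.3) with two sessions each. Section 1.1 gives "headache (14.8% vs. 16.2%" for active against sham. By its title in the reference list, the cited review concerns direct current stimulation. Reading its rate as per woman per session is an assumption.

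- Expected headache reports per phase session with no stimulation effect: 20 × 0.162 = 3.24.
- Over all 40 sessions: 40 × 0.162 = 6.48.
- At the active rate: 20 × 0.148 = 2.96 per phase session.
- Chance of at least one such report in a phase session: 1 − (1 − 0.162)^20 = 0.97.

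**4. The part a pre-session checklist could identify**

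A sham rate includes headaches that begin during the session. If a share *s* was present on arrival, the checklist identifies 3.24 × *s* per phase session. The documents do not give *s*. For assumed values:

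- *s* = 0.25: 3.24 × 0.25 = 0.81
- *s* = 0.50: 3.24 × 0.50 = 1.62
- *s* = 0.75: 3.24 × 0.75 = 2.43

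The limits are 0 and 3.24. The checklist would settle roughly one or two reports per phase session under these assumptions, and possibly none.

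**5. Room in the visit**

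40 minutes of stimulation plus two 8-minute EEGs: 40 + 2 × 8 = 56. The visit lasts up to 90 minutes, which leaves 90 − 56 = 34 for electrode placement, the existing interview and a checklist. Placement time is not stated.

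**The case against.** The best defence is that the plan already points towards onset. The interview asks about effects during the procedure, and the DRSP rule concerns symptoms that appear close to the session. The interview form is not in the documents and may ask when a symptom began. This has some force. Still, nothing described records the level on arrival, so onset would rest on recall at the end of the session.

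Second, few items are exposed. Five of the seven examples (tingling, flickering lights, itching, burning, scalp pain) are mainly sensations of stimulation. This stands, and it limits the point to about two items.

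Third, DRSP baseline material exists, and ratings begun after session 1 precede session 2. This also stands. A reader might infer that the trial has no same-phase somatic baseline at all. The documents do not support that: the data and the phase windows are there, and only their use in the somatic safety summary is missing.

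Fourth, a reader might infer that the luteal session will show a spurious excess of side effects, and might attach a probability to it. The documents do not support that either. They give no ratio of luteal to follicular background symptoms, and the pooled summary makes no contrast between phases. Any such figure would be built on assumptions alone.

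Last, this is a 20-woman pilot with descriptive safety reporting, and referral to the PI is already cautious. That is a fair reason to keep the priority low.

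**Conclusion.** The point holds in a limited form. No structured side-effect assessment before stimulation is described, and the safety summary does not separate the two phases. Without a sham arm, a headache or neck pain present on arrival can be counted as a possible tACS effect. For the DRSP somatic items, the shortfall is a missing link to ratings that already exist.

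The size is unknown. About 3 of 20 women per session would report headache without any tACS effect, if a sham rate from a review of direct current stimulation applies per woman per session to women with PMDD. How many of those would have arrived with it cannot be taken from the documents.

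The primary and secondary efficacy results are unaffected, and nothing here suggests that participants are less protected. That a later trial would rely on this tolerability record is an inference; sections 6 and 6.4 speak of that trial in terms of efficacy. The point is a cheap improvement of low priority.

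**What to change.** 1. Give the section 6.3 side-effect checklist immediately before as well as after each stimulation.
2. Report items that are new or worse than before stimulation, separately for the follicular and luteal sessions. List unchanged items alongside so that no report is lost.
3. Show DRSP somatic ratings descriptively beside the woman's own diagnostic-study ratings for the same phase. Do not set a threshold that must be exceeded, because it could label a real effect as expected.
4. Leave severity grading, monitoring during the session, referral to the PI, discontinuation and IRB reporting as they are.

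The cost is about two minutes per session (an estimate), or 2 × 40 = 80 minutes over the study, plus a lookup of existing ratings and a few sentences of protocol text. No extra staff are needed. There are two downsides: asking beforehand may prompt some later reports, and the diagnostic-study ratings may be some months old.
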